11. REFERENCES

Version date/#	Section #/page	Description of change (s)	Rationale for change
V1.4, 4/15/20	Section 11 Compensation	Patient stipend increase: visit 1 from \$20 to \$100 visit 2 from \$20 to \$150 visit 3 from \$20/100 to \$50/100	Increased enrollment
V1.5 5/21/2020		Visit 2: addition of anatomical imaging-no additional time	Anatomical images as reference for 3D MRF
09/01/2020	Section 3: Objective/Hypothesis Section 4: Recruitment Section 4.4.2 Study procedures	Addition of single pre-therapy scan for patients with low Mammprint scores	Patients with low Mammprint scores will not undergo chemotherapy, but will provide a useful genetic control group to compare with the existing cohort of breast cancer patients.
9/24/2020	Section 4.3 vulnerable populations	Rescinded previous attempt to include non-english speaking individuals	translated documents and translators not available

1. Introduction

There has been a growing trend towards using quantitative MRIs for early response assessment in oncology¹. Methods already utilized clinically for measuring treatment response in breast cancer include 1) size criteria, 2) diffusion weighted imaging (DWI) with calculation of Apparent Diffusion Coefficient and 3) Contrast-enhanced dynamic contrast enhanced MRI (DCE-MRI)²⁻⁴. While these techniques assess various tumor properties such as volume, cellularity and perfusion, these techniques have their own individual limitations. For example, a change in size requires at least 2-3 cycles of chemotherapy to be measurable and have a predictive value⁵. Waiting till at least 2-3 cycles or mid-therapy to detect non-response implies that patients might be subjected to unnecessary cycles of ineffective treatment. Thus earlier measures of treatment response are essential. While DWI and DCE-MRI in combination have shown to be useful for early prediction of treatment response^{6,7}, DWI is hampered by low signal-noise-ratio in breast imaging and the measured ADC is highly dependent on MR system parameters and b-values used⁸. DCE-MRI requires administration of contrast and quantitative analysis of DCE-MRI is complex and time-consuming. Moreover, the results from DCE-MRI are affected by physiological factors, acquisition technique and post-processing pharmacokinetic modeling used for analysis^{2,9,10}.

On the other hand, T1 and T2 relaxation times represent intrinsic tissue properties in MRI. Relaxometry, i.e. measurement of T1 and T2 relaxation times can also provide objective and reproducible information about pathology. Older studies showed that relaxation times differed between healthy breast tissue and breast cancers^{11,12} and could potentially be used to predict early response to chemotherapy¹³⁻¹⁵. However, relaxometry as a response assessment technique has not yet crossed the translational gap because it is technically difficult in breast and there is very limited evidence on breast relaxometry for response assessment. We developed a novel 3D Breast

Magnetic Resonance Fingerprinting (3D MRF) technique, which allows simultaneous estimation of both T1 and T2 relaxation times in a clinically feasible manner and in less than 6 minutes of scan time¹⁶. This is a volumetric acquisition technique that generates co-registered quantitative maps to characterize breast tumor and peritumoral and contralateral breast tissue.

[figure not shown]
2. Preliminary Studies:

Our preliminary work on 3D breast MRF has shown that there are significant differences in T1 and T2 relaxation times between tumor and normal breast tissue^{16, 17}. We scanned 12 women with biopsy proven breast cancer and the tumor T1 and T2 relaxation were longer compared to normal breast tissue (mean \pm SD, Tumor T1: 1156 ± 200 ms, Normal breast T1: 846 ± 388 ms, Tumor T2: 72 ± 14 ms, Normal breast T2: 48 ± 12 ms, $p = 0.039$ for T1, $p < 0.001$ for T2). In addition, we performed a repeat 3D MRF scan after one cycle of chemotherapy in 7 patients and patients with decrease in tumor size showed significant decrease in tumor T1 and T2 relaxation times while non-responders showed only a negligible change in tumor T1 and T2 relaxation times¹⁷ (Table 1). Figure 1 shows representative 3D breast MRF maps from one patient who was scanned before and after one cycle of chemotherapy. Thus we hypothesize that 3D MRF before, during and after chemotherapy can provide additional quantitative information about changes during treatment and may predict early response to chemotherapy.

Table 1: Pilot data showing greater % decrease in T1 and T2 relaxation times in patients showing treatment response after one cycle of chemotherapy compared to non-responders

4.1 Recruitment

Patients will be identified from clinical visits to UH Breast Surgery/Hematology-Oncology Clinics and Radiology and the MRI inpatient/outpatient schedules. Patients will be recruited for two different study cohorts:

1. Patients with biopsy proven cases of breast cancer who will undergo chemotherapy treatment. These subjects will receive 3 MRI scans: 1 before chemotherapy, Scan 2 one week to ten days after the first round of chemotherapy, Scan 3 after completion of chemotherapy.
2. The range of scores for MammaPrint is -1 to +1. Any score above 0 is considered low risk. Any patients who have scores 0.355 or above are considered Ultra Low Risk. Patients with biopsy proven cases of breast cancer who have had a low MammaPrint assessment will not be treated with chemotherapy prior to surgery as per clinical standard of care. These subjects will receive only one MRI scan before clinically indicated surgery and/or therapy.

We propose the following pathways for patient recruitment:

- for patients first seen at the Clinics, the treating physician (breast cancer surgeon/breast oncologist) will introduce the study and a flyer with key information about the study may be given to the patient. If the patient shows willingness to participate, the patient's MRN will be sent via UH email to the Radiology Research Coordinator for actual study consent on the day of the baseline diagnostic MRI at UHCMC.
- if the patient has already had a diagnostic scan elsewhere before visiting the Clinic and is still interested in participating in the study, they will be scheduled for a *research only* non-contrast MR Fingerprinting scan at UHCMC before starting chemotherapy.
- alternatively, for patients who are first scheduled for breast MRI at UHCMC Radiology department, consenting will be directly done on the day of MRI without a referral from the breast clinic.

We are requesting a HIPAA waiver to identify eligible patients before approaching them to participate in the study. To confirm study eligibility, we will access the Physician Portal to get information about the breast cancer diagnosis and pathology results.

Request for waiver of HIPAA authorization and waiver of consent: We are requesting a waiver of HIPAA authorization and waiver of consent for identifying and contacting patients in person and not a waiver of the consent for the research study as such. We intend to identify patients from physician portal, inpatient/outpatient MRI schedule and/or referred by treating physician for a clinically indicated breast MRI and contact them in person. There will be no improper use of or disclosure of PHI under this waiver. The investigator will take precautions to protect the subject's privacy and the confidentiality of the data pertaining to his/her participation in this research study. Only the research staff will access the PHI for above described purpose. The patient identifiers accessed under this waiver of HIPAA authorization will not be retained. The identifiers will be destroyed on the same day once the purpose of contacting the patients in person is complete. We assure that the PHI will not be reused or disclosed to (shared with) any other person or entity, except as required by law, for authorized oversight of the research study, or for other research for which the use or disclosure of the PHI would be permitted under the Privacy Rule. We are requesting a waiver of HIPAA authorization for contacting the patients in person and not a waiver of informed consent process for the study itself. For this purpose, the waiver of HIPAA authorization and waiver of consent is necessary for recruitment. We will not be able to meet our recruitment goals without this waiver.

Inclusion and exclusion criteria will be assessed for each potential study patient, and written informed consent will be obtained by qualified study personnel in a private setting at UHCMC.

We will also obtain contact information of the patients to schedule them for follow-up scans for assessing tumor response. We hope to get at least one-two eligible patients per week and recruit patients over the first eighteen months. Since the chemotherapy regime takes about 4-6 months to complete followed by surgery, we hope to get the complete information for the last patient recruited within 2 years of initiating the study

4.2 Inclusion/Exclusion Criteria

	Inclusion Criteria:
1.	Biopsy proven cases of breast cancer
2.	Women ages 18 and over

	Exclusion Criteria
1.	Patients with only benign lesion
2.	Patients with only ductal carcinoma in situ (DCIS)
3.	Patients with recurrent/ residual breast cancer in same breast
4.	Pregnant women
5.	Lactating Women
6.	Patients with ferromagnetic or otherwise non-MRI compatible aneurysm clips.
7.	The presence of an implanted medical device that is not MRI-compatible, including, but not limited to: pacemaker, defibrillator
8.	Patients with contraindications for MRI due to embedded foreign metallic objects. Bullets, shrapnel, metalwork fragments, or other metallic material adds unnecessary risk to the patient.
9.	Known history of severe claustrophobia.
10.	Patients under the age of 18
11.	For patients with known history of allergic reaction to MR contrast material or abnormal kidney function (GFR < 40 mL/ min), a contrast enhanced exam will not be performed; however, a non-contrast exam may be performed in these patients.

4.3 Vulnerable Populations

Illiterate individuals may be enrolled by having a witness present at the time of consent. The consent form will be read to the participant and they will sign the consent by making their mark in the signature section. A witness will be present to confirm the consent process has taken place; the witness will sign the consent document. We will not actively recruit students and employees of UH and CWRU, however, they will not be excluded from participation. UH/CWRU students and employees who may consider participation will be informed that their decision to participate will in no way influence their job or status in any way and study results will not be reported to their supervisor. We will not actively recruit student or employee populations, but they will not be excluded if they otherwise meet enrollment criteria.

Prisoners and many other vulnerable populations will be excluded from this study; these populations will not provide any unique information to the study and will not benefit from participation.

4.4 Methods

4.4.1 Breast MRI:

This is a prospective, longitudinal study comprising of pre-treatment baseline scan, interim scan after one cycle of chemotherapy and end-of-chemootherapy scans. The research sequence being evaluated is 3D MR Fingerprinting sequence. This is a painless technique that takes about 6 minutes to perform and does not have any risks or discomfort other than those associated with regular breast MRI. 3D MR Fingerprinting technique is also a non-contrast technique and generates quantitative information about MR-visible tumors without having to administer contrast. Since we propose to add 3D MR Fingerprinting sequence to regular clinical MRI scans ordered as part of standard of care, this would only add approximately 20 minutes to overall scan time. For patients who undergo research only 3D MR Fingerprinting scans, the entire scan time would be approximately 30 minutes, less than the time taken for regular clinical MRIs. All patients would be screened for MR Safety and Eligibility to eliminate any risks of undergoing MRI. For patients getting contrast (Gadavist®) for research purposes, the eGFR would be checked from patient records and contrast would only be administered to patients who have a documented eGFR > 40 ml/min/1.73 m² within the previous 3months.

4.4.2 Study procedures:

Radiology study personnel will obtain consent in the Radiology department prior to performing 3D MR Fingerprinting scans. Consent to participate will be obtained prior to performing any research scans:

Visit 1: 3D MR Fingerprinting images will be added to the clinical MRI scan before start of chemotherapy or before surgery for the MammaPrint cohort. The additional research images will take less than 20 minutes to acquire.

Visit 2: Patients receiving chemotherapy will be scheduled for a research only non-contrast 3D MR Fingerprinting and anatomical MRI scans 7- 10 days after the first cycle of chemotherapy. Acquisition of images will take approximately 30 minutes.

Visit 3: For patients receiving chemotherapy, if the treating physician orders a clinical MRI scan within 1 month of end of chemotherapy treatment, we will add a 3D MR Fingerprinting sequence to the clinical scan. The additional research images will take less than 20 minutes to acquire.

If the patient is not scheduled for a clinical scan within 1 month of end of chemotherapy treatment, we will contact the patient to schedule a research only 3D MR Fingerprinting scan. Breast cancer is hard to visualize on MRI post treatment, so we would like to administer IV gadolinium contrast for research purposes. Patients will be reconsented prior to the research only scan to determine whether or not they will receive IV contrast. If the patient declines

administration of contrast for the post treatment scan, we will perform a non-contrast scan. Acquisition of images will take 30-45 minutes.

Criteria for response assessment

Final surgicopathology results would be used for response assessment. Thus pathology reports with pT0N0 would be designated as pathological complete response while pT0 but with residual nodal deposits on pathology would be considered as primary tumor response for analysis purpose. Presence of any residual tumor on pathology would be considered as non-responder.

In the sub-group of patients who fail to undergo surgery at the end of treatment due to reasons beyond the control of study researchers, RECIST version 1.1 criteria would be considered as surrogate criteria for response (1). Thus no visible tumor and nodes at end of treatment scan will be considered complete response, >30% decrease in long-axis diameter (LAD) compared to baseline will be partial response, > 20% increase in LAD will be progressive disease while < 30% decrease/ > 20% increase in LAD will be considered stable disease.

All categories of response would be considered independently for analysis.

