11. COMPENSATION

Visit 1: Subjects will receive \$100 for research scan

Visit 2: Subjects will receive \$150 for non-contrast research scan

Visit 3: Subjects will receive \$50 for non-contrast research scan or \$100 for contrast research scan

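### For patients without surgery, imaging complete response is not tied to a contrast-enhanced scan, so residual disease missed on a permitted non-contrast Visit 3 scan can be labelled complete response

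*Combined protocol and SAP*

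**What the plan says.** Section 4.4.2 (Criteria for response assessment) makes pathology the standard: "Final surgicopathology results would be used for response assessment". For patients who do not have surgery, "RECIST version 1.1 criteria would be considered as surrogate criteria for response", and under that surrogate "no visible tumor and nodes at end of treatment scan will be considered complete response". The paragraph ends: "All categories of response would be considered independently for analysis".

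On the Visit 3 scan, the same section explains the research contrast: "Breast cancer is hard to visualize on MRI post treatment, so we would like to administer IV gadolinium contrast for research purposes". For a patient who declines "administration of contrast for the post treatment scan, we will perform a non-contrast scan". Section 4.2, item 11, adds that with contrast allergy or GFR below 40 "a contrast enhanced exam will not be performed; however, a non-contrast exam may be performed in these patients". Section 4.4.1 limits research contrast to patients with a documented eGFR above 40 in the preceding three months, so a missing recent value also leads to a scan without it. Section 11 (Compensation) prices both kinds of Visit 3: "Subjects will receive \$50 for non-contrast research scan or \$100 for contrast research scan".

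Section 6, item 3, compares changes between responders and non-responders as defined by the surgical pathology result. It does not say how patients classified only by RECIST enter the analysis. The data items in Section 5 include the MRI images but not whether contrast was given.

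**The concern.** A rule based on nothing being visible is only as good as the scan's ability to show what is there. The protocol asks for contrast because treated tumor is hard to see, then applies the rule unchanged to scans done without contrast. For an unoperated patient scanned that way, failure to see tumor and absence of tumor receive the same label.

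For the complete-response label the error can run in only one direction, from residual disease to complete response. It depends on contrast use, which follows patient preference, allergy and renal function rather than response. These patients have no pathology against which the label could be corrected. At stake is the validity of the imaging complete-response category and, if that category is merged with pathological response, some of the T1/T2 difference that the study is sized to detect.

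**Working it through.** **Text check.** Four conditions must hold together for a wrong label.

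1. The patient has no surgery. Section 4.4.2 provides for this.
2. Visit 3 is non-contrast. Sections 4.2, 4.4.1, 4.4.2 and 11 (Compensation) provide for this.
3. Residual disease is present.
4. It is not seen. The reason given for gadolinium makes this plausible.

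No section restricts the complete-response rule to contrast-enhanced scans, defines a not-evaluable category, or plans a sensitivity analysis by contrast use. The gap is in the text and does not depend on any figure.

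**The plan's own figures.** Section 6 gives a 25% change in responders, under 7% in non-responders, a difference of 18 points, alpha 0.05, power 80%, 62 evaluable and 124 recruited. The readable text gives no SD of the percentage change and no sidedness. Taking a two-sided test and an assumed SD of 25 points:

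n per group = 2 × (1.96 + 0.84)² × (0.25/0.18)² ≈ 30.3, rounded up to 31, total 62.

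This matches the plan. An SD of 20 points would give 40 in total and 30 points would give 88. Recruitment is 62/(1 − 0.5) = 124, as stated.

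**If imaging and pathological responders are pooled (assumed).** Let m be the share of called responders who have residual disease and change by 7% rather than 25%.

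- Difference = 18 × (1 − m) points.
- SD² in called responders = 0.25² + m(1 − m) × 0.18², averaged with 0.25² in non-responders.
- Power is two-sided 0.05, with 31 per group.

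| m | Difference (points) | Power |
|---|---|---|
| 0 | 18.0 | 81% |
| 5% | 17.1 | 76% |
| 10% | 16.2 | 71% |
| 20% | 14.4 | 60% |

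The documents do not give m. Write m = u × v × w, with these assumed ranges:

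- u, the share of called responders without surgery: 5–20%.
- v, the share of those with a non-contrast Visit 3: 25–100%.
- w, the share of those who are false complete responders: 20–40%.

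Then m runs from 0.05 × 0.25 × 0.20 = 0.25% to 0.20 × 1.00 × 0.40 = 8%. The difference runs from 18 × 0.9975 = 18.0 to 18 × 0.92 = 16.6 points, and power from 81% to about 73%.

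In counts, k misplaced patients joining 31 true responders give (31 × 25 + 7k)/(31 + k) − 7. That is 17.4 points for k = 1 and 16.4 for k = 3. If k = 0, nothing changes.

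**If the categories are kept apart.** The main comparison is untouched. Within the imaging complete-response category the mislabelled share is v × w, from 0.25 × 0.20 = 5% to 1.00 × 0.40 = 40% under the same assumptions. The error is concentrated in a small group.

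**The case against.** The strongest reply is that the main comparison is protected. Section 6 defines it by surgical pathology, which the patients under the surrogate rule do not have, and Section 4.4.2 treats the response categories separately. On that reading no imaging complete responder joins the pathological responders. This largely stands: dilution of the T1/T2 difference is possible, not shown. It does not close the matter. Section 4.4.2 introduces RECIST as a substitute for the pathology standard, and Section 6 never says whether patients classified that way are in or out. The label itself is unreliable on either reading.

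A second reply is that few patients can be affected. Section 7.2 makes contrast the default for a research-only Visit 3, the contrast scan is paid more, and some unoperated patients may already fall within the expected 50% attrition. This also stands, and the number could be zero.

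A third is that the protocol's remark on visibility concerns MRI after treatment in general, not non-contrast MRI in particular. That is correct as a matter of wording. The application to non-contrast scans is an inference, but a fair one, because the remark is offered as the reason for giving contrast.

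**Conclusion.** The gap is real and narrow. As written, an unoperated patient with an apparently clear non-contrast Visit 3 is a complete responder, although the protocol's own reason for using contrast casts doubt on that reading. This rests on the text alone.

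The size rests on assumptions. With pooling, an SD of 25 points and the ranges above, the loss is at most about 1.4 of 18 points (18.0 − 16.6), and about 8 points of power (81% to 73%). It is probably modest unless patients without surgery are common. Without pooling, the damage stays inside the imaging complete-response category.

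A reader might infer more, in two ways that the documents do not support. One is that the main T1/T2 comparison is biased as planned; that requires a pooling step which Sections 4.4.2 and 6 leave unsettled. The other is that every RECIST category errs toward response when contrast is missing. Diameters may be compared between scans with and without contrast, but nothing in the documents fixes the direction of that measurement error. The one-way argument covers only the complete-response label.

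**What to change.** In the surrogate paragraph of Section 4.4.2, state:

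> Imaging complete response is assigned only when the end-of-treatment scan is contrast-enhanced. In a patient without surgery, a non-contrast end-of-treatment scan on which no tumor or nodes are seen is response-not-evaluable. Residual tumor that is visible on a non-contrast scan still counts as not complete response.

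Add contrast use at Visit 3 to the data items in Section 5. In Section 6, state that the responder/non-responder comparison is confined to patients with surgical pathology, and that RECIST-classified patients are added only in a sensitivity analysis.

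The restriction should stop there. Making every unoperated patient with a non-contrast Visit 3 not evaluable would discard those with visible residual or growing tumor, who are informative. Requiring a contrast-enhanced baseline as well could exclude patients who, under Section 4.1, have only a non-contrast research scan at the study site before chemotherapy.

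The cost is a few sentences, one data item and a few unoperated patients who become not evaluable. Who receives contrast does not change. The change should be made before outcomes are classified, because setting such patients aside afterwards would be a post hoc choice.

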6. STATISTICAL CONSIDERATIONS

1. From the 3D MR Fingerprinting maps, T1 and T2 relaxation times will be obtained for tumor, and peritumoral and normal breast tissue at all three scans.
2. From routine MRI scans, the tumor size and tumor ADC will be obtained.
3. Changes in all quantitative measurements will be compared between responders and non-responders based on final surgical pathology and the predictive value of 3D MR Fingerprinting as compared to existing techniques would be assessed using appropriate t-tests and logistic regression analysis.

Sample Size Calculation: Based on our pilot data, we expect a 25% change in T1 and T2 relaxation times in responders and less than 7% change in non-responders with an effect size of 18% (0.18). At a significance level of 0.05 and power of 80%, the expected sample size is 62. Based on our pilot data, we also expect an attrition and drop-out rate of 50%, and thus total number of subjects recruited will be 124.

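### The LAD response cut-offs in Section 4.4.2 overlap and leave gaps, and the plan does not say whether patients classified by RECIST enter Section 6's pathology-based comparison

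*Combined protocol and SAP*

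**What the plan says.** Section 4.4.2 (Criteria for response assessment) bases response on final surgical pathology. A pT0N0 report is a pathological complete response. For a cleared breast with positive nodes the rule is "pT0 but with residual nodal deposits on pathology would be considered as primary tumor response for analysis purpose". The next sentence is "Presence of any residual tumor on pathology would be considered as non-responder".

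For patients who do not have surgery at the end of treatment, the same section says "RECIST version 1.1 criteria would be considered as surrogate criteria for response". Complete response is no visible tumor or nodes on the end-of-treatment scan. Partial response is an LAD decrease of more than 30% from baseline. The other two categories are defined together: "> 20% increase in LAD will be progressive disease while < 30% decrease/ > 20% increase in LAD will be considered stable disease". The section ends with "All categories of response would be considered independently for analysis".

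In Section 6, item 3, changes in all quantitative measurements are to be "compared between responders and non-responders based on final surgical pathology". The predictive value of MR Fingerprinting relative to existing techniques "would be assessed using appropriate t-tests and logistic regression analysis".

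**The concern.** The response label is the outcome in the Section 6 t-tests and logistic models, so each patient needs exactly one label and a known place in, or outside, the comparison. Three things stand in the way.

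- The printed LAD cut-offs give some patients two labels and others none.
- Section 4.4.2 gives patients without surgery a response, while Section 6 defines its groups by surgical pathology alone.
- The wording for node-only residual disease can be read two ways.

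If these are left open, the analysis set and the grouping can be settled after the T1 and T2 results are known. There is also a circularity. Section 6 collects tumor size and sets MR Fingerprinting against existing techniques, and the Introduction lists size criteria among the methods in clinical use. In a patient without surgery, LAD change defines the outcome, so size change cannot be tested fairly as a predictor of it.

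**Working it through.** The plan states no figure on this point to reproduce. The check applies the printed cut-offs and then compares the two sections.

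**1. LAD cut-offs.** Let x = 100 × (end-of-treatment LAD − baseline LAD) / baseline LAD, for patients not in complete response. As printed in Section 4.4.2:

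- partial response: x < −30
- progressive disease: x > 20
- stable disease: a decrease of less than 30%, or x > 20

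A decrease of less than 30% can be read literally, as a true decrease (−30 < x < 0), or as a signed change (any x > −30). The last column shows, for illustration only, the effect of reversing the sign so that stable disease is −30 < x < 20. Sizes are for an assumed 30 mm baseline: 30 × 0.70 = 21 mm at −30%, and 30 × 1.20 = 36 mm at +20%.

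| x | LAD (mm) | Literal reading | Signed reading | Sign reversed |
|---|---|---|---|---|
| −50% | 15 | partial | partial | partial |
| −30% | 21 | none | none | none |
| −10% | 27 | stable | stable | stable |
| 0% | 30 | none* | stable | stable |
| +10% | 33 | none | stable | stable |
| +20% | 36 | none | stable | none |
| +40% | 42 | progressive and stable | progressive and stable | progressive |

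*Stable if no change is counted as a decrease of less than 30%.

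The overlap above +20% is present on both readings of the printed text. The gap from 0% to +20% closes on the signed reading. Exactly −30% has no category in any column, because both inequalities that meet there are strict. Reversing the sign removes the overlap and the open interval, but leaves exactly +20% without a category for the same reason.

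**2. Who is analysed.** Section 4.4.2 supplies a stand-in response when pathology is missing. Section 6 admits only groups formed from pathology. Nothing in the available text maps complete response, partial response, stable disease or progressive disease to responder or non-responder, or says that these patients are left out. The mapping is not obvious. A partial response usually leaves visible tumor; on pathology any residual tumor means non-responder, yet the category is called a response.

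**3. Node-only residual disease.** The pT0-with-nodes sentence points to a responder. The next sentence speaks of any residual tumor on pathology without limiting it to the breast, so a nodal deposit can meet it. The two sentences allow the same patient to fall on either side.

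**The case against.** The LAD defect can be called typographical. Section 4.4.2 names RECIST 1.1, one reversed sign explains both the overlap and the 0% to +20% gap, and the sign may have been altered when the PDF was converted to text. The boundary at exactly −30% is a small matter. All of this lowers the weight of the point, but does not remove it: the text as supplied is a classification rule that cannot be applied as printed.

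The sections can also be reconciled in more than one way. The surrogate rule could be given a place in Section 6, which would avoid dropping patients. That is possible, but it would let LAD change be both outcome and predictor, and it would mix two standards of evidence: Section 4.4.2 itself says that cancer is hard to see on MRI after treatment, and it allows that scan to be done without contrast.

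Three stronger readings are tempting and are not supported.

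- A reader might infer that the study must be analysed in seven groups (three pathology plus four RECIST) and not two. Considering the categories independently may mean only that the pathology and RECIST sets are not pooled, which fits Section 6.
- A reader might infer that 62 is too small. The number without surgery is not given, and the plan does not say whether its 50% attrition allowance covers these patients, so no shortfall can be calculated.
- A reader might infer that the pilot difference does not carry over, because Section 2 describes the pilot patients by decrease in tumor size. The body of Table 1 and Section 3 were not in the text available for this review, and the pilot response definition may be there.

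**Conclusion.** The point holds as a defect of definition and of analysis set. As printed, every LAD increase above 20% has two labels. On the literal reading 0% to +20% has none, and exactly −30% has none on any reading. The effect is confined to patients without surgery, and its size in patients cannot be stated because the plan gives no count. The ambiguity for pT0 with residual nodes is separate and concerns patients who do have surgery.

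The gap between Sections 4.4.2 and 6 is an unstated rule on who enters the comparison; it is not a proven contradiction on the number of groups. The conclusion assumes that the supplied text reproduces the inequality signs correctly and that Section 3 holds no mapping of the categories. A mapping there would answer the second part, but not the overlap in the cut-offs. The point should be fixed before analysis. It gives no ground for saying that 62 is wrong.

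**What to change.** - Check the signs in the source PDF. Correct the stable-disease bound in Section 4.4.2 so that the four categories are mutually exclusive and cover every LAD change. Assign the boundary values −30% and +20% explicitly.
- In Sections 4.4.2 and 6, state one binary primary outcome from surgical pathology. Reword the non-responder sentence so that pT0 with residual nodes falls in one group only, consistent with its designation as a primary tumor response for analysis.
- State that RECIST-classified patients are outside the primary comparison. Use them only in a sensitivity analysis, with a stated mapping to responder and non-responder, that does not test tumor size as a predictor.

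The cost is a few sentences, with no change to visits or data collection. The downside is that patients without surgery leave the primary comparison. This loses some numbers, to an extent that the plan does not allow to be calculated, and may introduce selection if these patients differ from those operated on. The sensitivity analysis would show how far the result depends on leaving them out.
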